8.2.2.6. Time to first use of intensification or relaxation of hypoglycemic agent

Kaplan-Meier plots will be prepared for these endpoints by treatment. These endpoints will be analyzed using Cox proportional hazards models with treatment, region, baseline eGFR categories (<60 or ≥60 mL min⁻¹ per 1.73 m²), baseline BMI (< or ≥25 kg m⁻²), history of heart failure (yes or no), insulin use or not, and baseline HbA_{1c} as the covariates. Maximum likelihood with ties method of Breslow will be used. The hazard ratio of the endpoint, p-value with its two-sided 95% CIs presented. Subjects who withdraw from the trial and have post-baseline assessments will be censored at the last contact date. Subjects who have no follow-up event data will be censored at the date of randomization + 1 day. Analysis will also be conducted for subjects who have been prescribed insulin or sulfonylurea to control their diabetes. Time to first intensification of hypoglycemic agent will also be conducted for subjects who have been prescribed insulin or sulfonylurea to control their diabetes.

8.2.2.7. Time to hospitalization for heart failure and time to cardiovascular death or hospitalization for a heart failure event in all subjects and in subjects with a history of heart failure

Same analyses in Section 8.2.2.6 will be conducted. History of heart failure will not be used in the analysis model in subjects with a history of heart failure.

9. SAFETY

The safety endpoint of the program-wide meta-analysis is the hazard ratio for the time to first occurrence of adjusted MACE+. The analysis of this endpoint will not be discussed in this SAP.

The other safety endpoints include:

- Time to a 5-point composite adjudicated endpoint of CV death, non-fatal myocardial infarction, non-fatal stroke, hospitalization for unstable angina, or coronary revascularization
- Time to a 6-point composite adjudicated endpoint of CV death, non-fatal myocardial infarction, non-fatal stroke, hospitalization for unstable angina, hospitalization for heart failure, and coronary revascularization; and time to onset of event
- Time to individual events including all-cause mortality, CV death, non-fatal MI, non-fatal stroke, transient ischemic attack, hospitalization for unstable angina, hospitalization for heart failure, and coronary revascularization; and time to onset of each event
- Incidence of treatment emergent AEs (TEAEs) of interest
- Incidence of amputations
- Change from baseline in eGFR by study visit
- Change from baseline in UACR by study visit

Note that analysis for time to event endpoints (ie, first 3 bullets as listed above) will be included in a meta analysis plan, and not be included in this SAP.

Additional safety endpoints will also include:

- Incidence of all TEAEs
- Change from baseline as well as shift in clinical laboratory findings
- Change from baseline in vital signs measurements including orthostatic blood pressure
- Incidence of abnormal physical examination findings by body system
- Incidence of concomitant medication use

The analysis population used for safety analyses will be the Safety Analysis Set.

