9 PLANNED STATISTICAL METHODS

9.1 General Considerations

The following sections provide a summary of the planned analysis of the trial but a full analysis plan will be developed as a separate document and will become the final plan. All statistical analyses will be performed using SAS Version 9.4 or higher.

Data summaries will use descriptive statistics (number of subjects [N], mean, standard deviation [SD], Q1, median, Q3, minimum, and maximum) for continuous variables, and frequency and percentage of subjects for categorical and ordinal variables. If there are missing values, the number missing will be presented, but without a percentage.

Unless otherwise specified, all tests will be two-tailed using a 0.05 level of significance. All confidence intervals (CIs) will be two-sided 95% confidence intervals.

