MMRM ANCOVA will be used for the analyses of changes from baseline in eGFR in a similar manner as for the secondary endpoints. Least squares mean treatment differences between each bexagliflozin group and placebo will be estimated from the model with the two-sided 95% CIs presented.

The time to event onset will be analyzed using the Cox proportional hazards model with treatment and randomization stratification factors as the covariates. For each endpoint, the hazard ratio and its 95% confidence interval comparing bexagliflozin to placebo will be presented. Subjects who dropped out of the trial and for whom no follow up event data were collected (i.e., lost to follow-up subjects) will be censored at the last known follow-up.

Additional sensitivity analyses may also be conducted for subjects who enrolled prior to inclusion criteria modification separately from subjects who enrolled post inclusion criteria modification to assess a potential impact of subject population differences within the study due to inclusion criteria adjustment.

Additional safety endpoints will also include:

- Incidence of all TEAEs
- Change from baseline as well as shift in clinical laboratory findings
- Change from baseline in vital signs measurements including orthostatic blood pressure
- Incidence of abnormal physical examination findings by body system
- Incidence of concomitant medication use

AEs that begin after the first administration of double-blind study medication or existing AEs that worsen after the first dose of double-blind study medication will be considered TEAEs. The number and percentage of subjects reporting TEAEs will be summarized for each treatment group by MedDRA system organ class and preferred term, then by severity, and by relationship to study treatment. Drug-related AEs will be considered those to be at least possibly related to investigational product based on the investigator's assessment. The number and percentage of subjects reporting SAEs, and the number and percentage of subjects reporting AEs leading to treatment discontinuation will also be summarized for each treatment group by MedDRA system organ class and preferred term. By-patient listings will be provided for deaths, SAEs, and events leading to discontinuation of treatment.

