9.4. LABORATORY EVALUATIONS

Laboratory tests will include hematology panel, chemistry panel, serum lipids, and urinalysis testing. Hematology, chemistry, serum lipids, and urinalysis will be performed at the following time points: at the screening visit (Week -2 to -5), at week 0, 6, 12, 24, 36, 48 from screening to week 48, at every 24 weeks after week 48 to end of study, at end of treatment visit and follow up (4 weeks after end of treatment visit) visit. Renal functional testing by UACR will be determined at screening visit (Week -2 to -5), at week 0, 24, 36, 48 from screening to week 48, at every 24 weeks after week 48 to end of study and end of treatment visit. The study staff will contact each subject prior to a scheduled clinic visit to confirm the time of the visit and to remind the subject of proper fasting practice. A subject must be queried to assess compliance with an approximately 10-hour fast prior to blood draw to ensure the FPG and triglycerides values can be accurately determined. If a subject has not fasted for approximately 10 hours, the subject must return as soon as can be arranged (within 1 week) to provide a specimen after proper fasting. A list of laboratory tests is included in Table 8.

Low density lipoprotein cholesterol (LDL-C) will be calculated by the Friedewald equation. Direct LDL-C will be determined in subjects whose triglycerides are $> 350 \text{ mg dL}^{-1}$ at the screening visit. All subsequent LDL-C of these subjects will be determined by direct LDL-C measurements only. The following algorithm will be used to obtain LDL-C values for the analyses:

1. Select subjects (based on the SI unit) who have screening triglycerides $>3.4 \text{ mM}$ or $>350 \text{ mg dL}^{-1}$ based on the laboratory value reported
2. Take the LDL - direct measurement values only, throughout the study visits for those subjects
3. If screening triglycerides > 350 and no direct LDL-C values have been determined, take the calculated.

Among those subjects who have screening triglycerides >350 and have both calculated and direct LDL values, only take the direct LDL.

Urinalysis microscopy will be conducted if the subject has a positive result on the leukocyte esterase or nitrite dipstick tests to clarify the significance of the finding. Results of glucose measurement in the urinalysis must be suppressed from the

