laboratory reports so the sponsor, investigators, study coordinators, pharmacists, study subjects, and the adjudication committee members will remain blinded to the dosing assignment.

The baseline value for all laboratory tests will be the latest value obtained on or prior to Day 1. Change from baseline for all continuous parameters will be calculated as the post-baseline value minus the baseline value. All continuous variables will be summarized by number of subjects [n], mean, SD, Q1, median, Q3, minimum and maximum and categorical variables will be summarized by frequency and percentage.

Observed values (in SI units) and change from baseline over time will be summarized by treatment arm. Laboratory data will be classified as low, normal, or high relative to the parameter's reference range. Laboratory abnormalities for each treatment will also be summarized with shift tables for selected parameters.

For hematology, chemistry, and serum lipids, columns will be included for normal ranges and individual abnormal laboratory values will be flagged and clinical significance will be indicated.

Urine albumin/creatinine ratio (UACR) will be summarized and analyzed separately. Descriptive statistics for geometric mean, geometric coefficient of variation (gCV), median, Q1, Q3, minimum, and maximum of UACR values will be presented at screening, baseline, and all post-baseline scheduled visits for all subjects and for baseline macroalbuminuria subjects ($>300 \text{ mg g}^{-1}$). UACR data is left-skewed and will be natural log transformed first. Change in log transformed UACR from baseline to week 24 will be analyzed by ANCOVA model. The fixed effect will include region, baseline HbA_{1c} level as continuous variable, region, baseline eGFR categories (<60 or $\geq 60 \text{ mL min}^{-1} \text{ per } 1.73 \text{ m}^2$), baseline BMI ($<$ or $\geq 25 \text{ kg m}^{-2}$), history of heart failure (yes or no), insulin use or not, and treatment. The log transformed baseline values will be used as covariate. Analysis will be repeated for baseline macroalbuminuria subjects. LS means for each treatment will be estimated at week 24. The adjusted geometric mean ratio of relative change from baseline in UACR (the ratio of the week 24 geometric mean and baseline geometric mean) and the corresponding two sided 95% CI by treatment arm will be calculated as the antilog of the LS mean and 95% CI of log transformed values, converted to percentage.

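### The SAP keeps change in eGFR as a safety endpoint but omits the between-arm MMRM that protocol 9.6.4 plans for it, and SAP 12 does not declare the change

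*Combined protocol and SAP*

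**What the plan says.** Protocol 9.6.4 lists change in eGFR by visit as a safety endpoint and states how to analyze it: "MMRM ANCOVA will be used for the analyses of changes from baseline in eGFR in a similar manner as for the secondary endpoints". It also names the output: "Least squares mean treatment differences between each bexagliflozin group and placebo will be estimated from the model", with two-sided 95% intervals.

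Protocol 9.1 says that its statistical section is a summary and that "a full analysis plan will be developed as a separate document and will become the final plan".

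The SAP keeps the endpoint. SAP 4.3 has eGFR change among the key safety endpoints, and SAP 9 lists "Change from baseline in eGFR by study visit". The only deferral in SAP 9 concerns other endpoints: "Note that analysis for time to event endpoints (ie, first 3 bullets as listed above) will be included in a meta analysis plan".

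SAP 9.4 treats laboratory values descriptively: "Observed values (in SI units) and change from baseline over time will be summarized by treatment arm". The one laboratory variable with a model is the urine albumin:creatinine ratio (UACR): "Change in log transformed UACR from baseline to week 24 will be analyzed by ANCOVA model".

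On timing, SAP 9.4 says that hematology, chemistry, lipids and urinalysis are done "at week 0, 6, 12, 24, 36, 48 from screening to week 48", and at later visits.

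**The concern.** A comparison that the protocol specifies for a key safety endpoint has no counterpart in the governing plan, and nothing tells the reader that it was dropped. Whether to model eGFR, and with which covariates and visits, would then be open to decision after unblinding.

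The endpoint matters in this trial. The drug inhibits a renal transporter and has a modest diuretic effect (protocol 1 and 3.3.2). Subjects are admitted down to an eGFR of 45 mL/min/1.73 m², and up to 400 may have heart failure. Randomization is stratified at an eGFR of 60, and renal failure is an adverse event of special interest. The SAP gives by-visit treatment differences with intervals to exploratory weight and SBP (SAP 8.2.2.3) but not to eGFR.

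**Working it through.** The documents state no SD, power or target difference for eGFR, so there is no figure of the plan's to reproduce. The check is a comparison of texts.

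| Question | Protocol | SAP |
|---|---|---|
| Is eGFR change an endpoint? | Yes, 9.6.4 | Yes, 4.3 and 9 |
| Is a model given? | Yes, MMRM ANCOVA (9.6.4) | No. In 9.4 eGFR enters only as a baseline category in the UACR model |
| Is a between-arm difference with interval named? | Yes, 9.6.4 | No |
| Is it deferred to another plan? | No | No. Section 9 defers only its first three bullets, all time-to-event |
| Is the removal declared? | Not applicable | No |

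**What SAP 12 declares.** It lists the switch from FAS to ITT for the per-protocol set, the use of baseline eGFR group and continuous HbA1c as covariates in place of screening strata, the new primary analysis, and the added exploratory objectives and endpoints. eGFR appears there only as a covariate.

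**What remains for eGFR.** SAP 9.4 promises observed values and change from baseline by arm for laboratory data, which can reasonably be read to include eGFR. That gives per-arm means and SDs by visit, but no adjusted difference and no interval.

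**Which equation.** The SAP names none for the analysis. Protocol exclusion criterion 18 uses MDRD for eligibility.

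**Week 6.** Protocol Appendix 2 and SAP Table 4 agree. Chemistry, hematology and lipids are marked at V1, V3, V6, V8 to V10, V12 onward, EV and FU, and are blank at V5 (week 6). Urinalysis is marked at V5. The SAP 9.4 sentence is therefore right for urinalysis and wrong for the other three. The first scheduled post-dose creatinine is at week 12.

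**Illustration of what the omitted contrast could show.** This assumes an SD of eGFR change of 6 to 14 mL/min/1.73 m², which is not in the documents. It uses an unadjusted comparison of 1100 and 550 subjects with 6.5% annual withdrawal.

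- Fraction remaining at week 24: 0.935^(24/52) = 0.969.
- SE = SD × √(1/550 + 1/1100) / √0.969. At SD 10 this is 0.522 / 0.985 = 0.530.
- 95% half-width = 1.96 × SE: 0.62 at SD 6, 1.04 at SD 10, 1.46 at SD 14.
- Difference detectable with 90% power (two-sided 0.05) = (1.960 + 1.282) × SE: 1.03, 1.72 and 2.41 respectively.

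Over that range of SDs, the trial could estimate a week-24 eGFR difference to within about 0.6 to 1.5 mL/min/1.73 m².

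**The case against.** The strongest reply is that little is lost. The protocol sentence still stands, the endpoint is outside the testing hierarchy, the samples are taken anyway, and a crude difference could be worked out from the per-arm summaries. It is true that no data are lost and that the primary and key secondary results are untouched. But the protocol gives way to the SAP, and a hand-derived crude difference is not the adjusted repeated-measures estimate that the protocol specified.

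A reader might also infer more than the documents support:

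- *That the trial's renal effect as a whole gets no between-arm analysis.* The week-24 UACR ANCOVA includes treatment, although its named outputs are per arm. Renal failure events are summarized by arm with rates per 100 patient-years (SAP 9.3.3 and 9.3.3.1). The gap is in eGFR.
- *That the week-6 discrepancy causes the gap.* It has no bearing on a comparison at week 12 or later.
- *That eGFR escapes even the descriptive summaries because SAP Table 8 omits it.* Table 8 lists assays and includes creatinine, from which eGFR is calculated. Protocol Table 1 omits eGFR too, yet the protocol plans its MMRM.
- *That a week-6 row would be empty for every subject.* SAP 6.4 maps unscheduled and early-termination visits to windows, with days 1 to 63 assigned to week 6, and protocol 7.6 includes chemistry at early termination. The row would be sparse rather than necessarily empty.
- *That the off-drug follow-up samples go unused.* SAP 6.4 defines a follow-up window for laboratory data, so descriptive summaries can include it. A formal contrast there was never in the protocol.

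**Conclusion.** The point holds for eGFR. The protocol's between-arm MMRM is absent from the SAP and its removal is undeclared. Under the SAP, none of the scheduled post-baseline chemistry visits has a planned estimate of the eGFR difference or an interval. The most that follows from its text is a descriptive summary by arm.

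This should be corrected, because a protocol-specified comparison of a key safety endpoint has dropped out without notice. It does not threaten the primary or key secondary conclusions.

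The conclusion assumes that the SAP governs, as protocol 9.1 says, and that no other document supplies the analysis. The table shells that the SAP mentions and the meta-analysis plan were not available to check. An eGFR model in the shells would reduce the practical loss, but the SAP text would still need to specify it. The precision figures depend on an assumed SD and are illustrative only.

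The week-6 laboratory listing is a separate clerical inconsistency.

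**What to change.** 1. In SAP 9.4, restore the protocol's MMRM for change from baseline in eGFR, with baseline eGFR as covariate. Report the least squares mean difference and two-sided 95% CI at weeks 12, 24, 36 and 48 and at each later clinic visit with chemistry. State the equation; MDRD is the one that the protocol uses for eligibility.
2. If the sponsor prefers not to run this model, declare and justify its removal in SAP 12.
3. Optional, and beyond the protocol: a between-arm comparison at the off-drug follow-up visit, and a repeat by baseline eGFR below 60 and at or above 60.
4. As a separate minor correction, reconcile the week-6 listing of hematology, chemistry and lipids in SAP 9.4 with SAP Table 4 and protocol Appendix 2.

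The cost is SAP wording and a few extra tables from data already collected. The change should be made before unblinding.

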9.5.2 Handling Dropouts, and Missing Data

Discontinuation criteria are explained in [Section 6.13](#). Subjects who withdraw consent to participate in the study will not be replaced.

The early termination rate is estimated to be 6.5% annually. To the extent possible, attempts will be made to minimize the amount of missing data through measures planned in the study conduct. But if data are missing for the primary endpoint and the first key secondary endpoint (ie, change of HbA1c for subjects who have been prescribed insulin), they will be handled as follows:

1. All observed data will be analyzed and data obtained after rescue will not be excluded and considered as missing. This will be considered the primary analysis.
2. Missing primary efficacy endpoint information will be imputed via multiple imputation linear regression approach. A total of 10 imputed datasets will be generated, and the corresponding primary analyses will be carried out on each imputed dataset for each endpoint; the analyses results will be combined across the 10 datasets using the standard techniques for multiply imputed data sets in order to yield overall treatment comparison results on the imputed data for each endpoint.

The number, timing, pattern, reason for and possible implications of missing values in efficacy assessments will be investigated. The dropout patterns will be assessed by Kaplan-Meier plots if applicable to assess whether they differ between treatment groups.

The handling of missing safety endpoint (MACE+) data is described below in section 9.6.3; however, analyses on MACE+, while being collected in C-476, will only be formally analyzed in the meta-analysis.

For all other endpoints, the missing data will not be imputed and only the observed data will be used in the analyses.

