9.6.4 Other Safety Endpoints

The other safety endpoints include

- Time to a 5-point composite adjudicated endpoint of CV death, non-fatal MI, non-fatal stroke, hospitalization for unstable angina, or coronary revascularization
- Time-to a 6-point composite adjudicated endpoint of CV death, non-fatal MI, non-fatal stroke, hospitalization for unstable angina, hospitalization for heart failure, and coronary revascularization; and time to onset of event
- Time to individual events including all-cause mortality, CV death, non-fatal MI, non-fatal stroke, transient ischemic attack, hospitalization for unstable angina, hospitalization for heart failure, and coronary revascularization; and time to onset of each event
- Incidence of treatment emergent AEs (TEAEs) of interest
- Incidence of amputations
- Change from baseline in eGFR by study visit
- Change from baseline in UACR by study visit

AEs of special interest include the following categories:

- Genital mycotic infections
- Urinary tract infections including urosepsis and pyelonephritis
- Diuretic effects including hypovolemia
- Hypotension episodes
- Hepatotoxicity
- Hypoglycemia
- Falls and fractures
- Malignancies

- Hypersensitivity reactions
- Acid-base disorders including DKA
- Renal failure events

AEs of special interest will be defined programmatically based on MedDRA system organ class and preferred terms which will be predefined by a blinded medical reviewer and will be specified in the Statistical Analysis Plan.

Event terms, signs, and symptoms will be documented in the listings. The number and percentage of subjects who have experienced treatment emergent adverse events (TEAEs) of special interest will be summarized for each treatment group by type of AE. A TEAE is an AE that started or worsened in severity at or after start of randomized treatment.

A case report form for adverse events that require amputation will be completed to capture the date and type of procedure, anatomic location, and causes. The number and percentage of subjects experienced any TEAE that requires amputation will be summarized for each treatment group by type of events. The incidence of lower extremity amputation per 100 patient years will also be summarized. Additional analyses will be specified in the statistical analysis plan to evaluate potential risks in subpopulations based on age, gender, or other baseline characteristics (if sample size allows).

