10.9 Cardiovascular Endpoint Committee

An independent CEC has been established to prospectively adjudicate, in a blinded fashion, major cardiovascular events. These events will include CV mortality, MI, stroke, hospitalization for HF, acute coronary syndrome, urgent revascularization procedures, and possibly other endpoints. The CEC will have access to relevant CRFs, site data, hospital records, imaging studies, ECG records, or other laboratory testing results but will remain blinded to the subject treatment assignment throughout the entire development program. The end point definition is described in a separate CEC Manual of Operation.

The protocol specific safety and efficacy analyses will be conducted based on the adjudicated CV events documented by the CEC. A separate meta-analysis will be performed after all controlled phase 2/3 clinical trials are completed and will include all CEC adjudicated end

points for the analyses that will be prospectively defined in a meta-analysis plan. The event terms determined by the CEC will not be reconciled with the Investigators' assessment in each phase 2/3 study protocol.

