4.3. SAFETY ENDPOINTS

The key safety endpoints include:

- A 5-point composite endpoint of CV death, non-fatal myocardial infarction, non-fatal stroke, hospitalization for unstable angina, or coronary revascularization
- A 6-point composite endpoint of CV death, non-fatal myocardial infarction, non-fatal stroke, hospitalization for unstable angina, coronary revascularization or hospitalization for heart failure
- Individual events including all-cause mortality, CV death, fatal and non-fatal myocardial infarction, fatal and non-fatal stroke, hospitalization for unstable angina, hospitalization for CHF, or coronary revascularization. Both first events and total events, taking account of repeat events will be examined
- Change in eGFR from baseline
- Change in UACR from baseline
- Incidence of adverse events of interest. Adverse events of interest including urinary tract infections (UTI), pyelonephritis urosepsis, genital mycotic infections (GMI), diuretic effects including hypovolemia, hypotension episodes, hypoglycemia, hepatotoxicity, fractures, malignancies, hypersensitivity reactions, acid-base disorders including diabetic ketoacidosis, rash, renal failure events, and amputations

Other safety endpoints include:

- Adverse events
- Clinical laboratory events
- Physical examinations
- Vital signs including orthostatic blood pressure
- Use of concomitant medications

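### Protocol 9.6.4 promises study-level hazard ratios for the cardiovascular safety endpoints; a Note in SAP 9 defers them to a meta-analysis plan, and SAP 12 does not list the change.

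*Combined protocol and SAP*

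**What the plan says.** Protocol 9.6.4 lists three groups of time-to-event safety endpoints for this study. The first is "Time to a 5-point composite adjudicated endpoint of CV death, non-fatal MI, non-fatal stroke, hospitalization for unstable angina, or coronary revascularization". The second is a 6-point composite that adds heart failure hospitalization. The third is "Time to individual events including all-cause mortality, CV death, non-fatal MI, non-fatal stroke, transient ischemic attack, hospitalization for unstable angina", continuing with heart failure hospitalization and coronary revascularization.

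The method and output are then fixed: "The time to event onset will be analyzed using the Cox proportional hazards model with treatment and randomization stratification factors as the covariates", and "For each endpoint, the hazard ratio and its 95% confidence interval comparing bexagliflozin to placebo will be presented".

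The protocol sets only MACE+ apart. Protocol 9.5.2 says "analyses on MACE+, while being collected in C-476, will only be formally analyzed in the meta-analysis", and Protocol 9.2 rules out a formal non-inferiority test of MACE+ within the study. Protocol 10.9 keeps the study's own analyses distinct from the separate meta-analysis: "The protocol specific safety and efficacy analyses will be conducted based on the adjudicated CV events documented by the CEC".

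SAP 4.3 still calls the two composites and the individual events key safety endpoints, and adds "Both first events and total events, taking account of repeat events will be examined". SAP 9 repeats the three groups from Protocol 9.6.4 and then states "Note that analysis for time to event endpoints (ie, first 3 bullets as listed above) will be included in a meta analysis plan", adding that they are outside this SAP. SAP 12, the section for changes from the protocol, has no entry for this.

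**The concern.** The SAP names these endpoints as key and then provides no time-to-event analysis for most of them. Protocol 9.1 makes the separate analysis plan the final one, so the Note governs what will be produced.

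This is an event-driven trial in patients at high cardiovascular risk, and one of its stated safety objectives is to evaluate at least 52 weeks of exposure in that population. Under the SAP as written, the study's planned outputs contain no hazard ratio or interval comparing the arms on all-cause death, cardiovascular death alone, MI, stroke, TIA, unstable angina, revascularization or either composite. A pooled estimate across the program answers a different question from the study-level estimate that the protocol promised. A reader who relies on SAP 12 for the departures from the protocol would not learn of this one.

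**Working it through.** **1. What is promised and what remains**

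| Endpoint | Protocol 9.6.4 | SAP |
|---|---|---|
| 5-point composite | Cox HR, 95% CI | Deferred by the Note in SAP 9; not named in SAP 9.3.3.3 |
| 6-point composite | Cox HR, 95% CI | Deferred; not named in SAP 9.3.3.3 |
| All-cause death | Cox HR, 95% CI | Deferred; SAP 9.3.3.3 lists cardiovascular mortality only |
| CV death, non-fatal MI, non-fatal stroke, TIA, unstable angina, revascularization | Cox HR, 95% CI | Deferred; number, percentage and rate per 100 patient-years of adjudicated events (SAP 9.3.3.3) |
| HF hospitalization | Cox HR, 95% CI | Cox HR, 95% CI and Kaplan-Meier plot, as exploratory efficacy (SAP 8.2.2.7) |

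SAP 8.2.2.7 also covers cardiovascular death or HF hospitalization as a combined endpoint. For all-cause death, the SAP otherwise offers only adverse events leading to death (SAP 9.3.2) and a count of subjects whose vital status was determined (SAP 7.1).

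The crude rates do not replace a time-to-first-event analysis. Patient-years run from first dose to end of study (SAP 6.2.6), not to the first event. SAP 9.3.3.1 puts the total number of events in the numerator.

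**2. What SAP 12 lists**

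The per-protocol set is drawn from ITT instead of FAS. Baseline eGFR group and continuous baseline HbA1c replace the screening strata. The primary analysis uses imputation based on retrieved dropouts. Two exploratory objectives and their endpoints are added. The deferral of the Cox safety analyses is not there.

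**3. Precision the restored analyses would have**

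Inputs are the 2-year rates in Protocol Table 2 (Table 1 in SAP 3.7), applied to 1250 subjects without and 400 with prior heart failure, and the 2:1 allocation. First, the table's own counts:

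- Death: 0.035 × 1250 = 43.75 and 0.088 × 400 = 35.2, so 44 + 35 = 79.
- CV death: 0.023 × 1250 = 28.75 and 0.073 × 400 = 29.2, so 29 + 29 = 58.
- MI: 0.032 × 1250 = 40 and 0.045 × 400 = 18, so 58.
- Stroke, and unstable angina: 0.010 × 1650 = 16.5 each; the table shows 16.

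The counts reproduce. With d events at 2:1 and a hazard ratio near 1, the variance of the log hazard ratio is 1/(d × 2/3 × 1/3), so SE = √(9/(2d)). The 95% limits are the hazard ratio multiplied and divided by exp(1.96 × SE).

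| Endpoint | d | SE | Factor | 95% CI at HR 1.0 |
|---|---|---|---|---|
| All-cause death | 79 | 0.239 | 1.60 | 0.63 to 1.60 |
| CV death | 58 | 0.279 | 1.73 | 0.58 to 1.73 |
| MI | 58 | 0.279 | 1.73 | 0.58 to 1.73 |
| Stroke | 16 | 0.530 | 2.83 | 0.35 to 2.83 |
| Unstable angina | 16 | 0.530 | 2.83 | 0.35 to 2.83 |

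The documents give no revascularization or TIA rate, so no figure is offered for those events or for the two composites.

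**The case against.** The strongest defence is that the move is open. The Note states it plainly, Protocol 9.1 lets the SAP supersede the protocol's summary of analyses, and Protocol 10.9 already says the meta-analysis will include all CEC-adjudicated endpoints. On that view the fault is a missing line in SAP 12. This stands in part: nothing is concealed. But the Note does not identify itself as a departure from Protocol 9.6.4 and gives no reason. Nor does including these events in the meta-analysis require dropping them from the study, since Protocol 10.9 provides for both.

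Four stronger readings are tempting, and the documents do not support them.

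- **That all cardiovascular time-to-event analysis has gone.** HF hospitalization keeps its Cox model, as does CV death or HF hospitalization.
- **That no study-level hazard ratio will exist for the deferred endpoints.** The meta-analysis plan has not been seen and could contain one. The supportable statement is that the SAP neither provides these estimates nor says where they will appear.
- **That the SAP took away the MACE+ analysis.** The protocol had already assigned it to the meta-analysis, so its precision is not part of what the Note removes.
- **That repeat events have no method at all.** SAP 9.3.3.1 gives a rate based on total events, and SAP 9.3.3.3 places adjudicated events in the same table. That is descriptive, but the protocol promised no recurrent-event model.

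It is also fair that stroke and unstable angina, at 16 projected events each, would be estimated very imprecisely. That limits what those two hazard ratios can show, but it is not a reason to drop the estimates for death, CV death, MI and the composites.

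Finally, study-level results might be thought to compromise the later meta-analysis. The SAP already produces adjudicated event rates by arm and some Cox results. Aggregate estimates reveal no individual assignments to the CEC.

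**Conclusion.** The point holds as a discrepancy between protocol and SAP that changes what the study's planned outputs can show. Study-level hazard ratios promised in Protocol 9.6.4 are deferred for both composites and for every listed individual event except HF hospitalization. SAP 12 neither lists nor justifies this.

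On the plan's projections, the estimates at issue would carry 95% limits of the hazard ratio multiplied and divided by 1.60 for all-cause death, 1.73 for CV death or MI, and 2.83 for stroke or unstable angina. These factors assume that the 2-year counts in Table 2 are realized, that each count is of subjects with a first event, that events split about 2:1 (hazard ratio near 1), and that the table's MI and stroke rows approximate the non-fatal endpoints. Treatment lasting beyond two years would add events and narrow the intervals. The textual finding depends on none of these figures.

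**What to change.** Remove the Note in SAP 9 and write in the Protocol 9.6.4 analyses:

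- **Endpoints:** 5-point composite, 6-point composite, all-cause death, CV death, non-fatal MI, non-fatal stroke, TIA, hospitalization for unstable angina and coronary revascularization. HF hospitalization is already covered by SAP 8.2.2.7.
- **Data:** first events as adjudicated by the CEC, in the Safety Analysis Set.
- **Model:** Cox regression with the covariates of SAP 8.2.2.6, which follow SAP 12 in using baseline eGFR group and continuous baseline HbA1c.
- **Output:** hazard ratio, 95% CI and Kaplan-Meier curve for each endpoint, with no non-inferiority test. Formal MACE+ analysis stays in the meta-analysis.

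If any endpoint is still deferred, list it in SAP 12 with the reason and the place where the study-level hazard ratio will be reported.

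The cost is SAP wording and a few additional outputs, because the Cox specification already exists in SAP 8.2.2.6 and 8.2.2.7. Sample size, alpha and trial conduct do not change. The small downside is that hazard ratios from this study will exist before the meta-analysis, but Protocol 10.13 already bars publication until the meta-analysis is complete.
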